### 9.2.3 End of Study (or Early Discontinuation) Procedures

On completion of treatment at Month 36 or earlier if subject is discontinued/withdrawn early, all assessments for Visit 23 (End of Study or Early Termination) will be completed per the [Schedule of Events](#). See also Section 5.5, [Withdrawal of Subjects](#), for further information on withdrawal procedures and criteria.

The following assessments for the end of study visit will be performed:

- SF-36
- Abbreviated physical examination (including body weight)
- Vital signs (BP, pulse, temperature)
- Standard 12-lead ECG
- Blood sample collection for analysis at central laboratory
- Serum pregnancy testing
- FMV
- 24-hour urine sample collection (**IMPORTANT:** 24-hour urine collection will have to begin 2 days prior to Month 36 visit in order not to coincide with the FMV sampling due on the day of this visit)
- Concomitant medication
- AEs
- SELENA-SLEDAI
- Returned capsule count and drug accountability
- Confirmation of completion/discontinuation using IRT
- Information for the HRU assessment will be collected and recorded

### 9.2.4 Follow-up Procedures

All subjects will have a safety follow-up visit after the last dose of study drug at Month 37 ( $\pm 10$  days), to collect any new AEs and concomitant medications. This visit (Visit 24) will be

conducted as an in-clinic visit. An assessment of vital status will also be conducted at 6 and 12 months post study.

Assessments for the follow-up visit are as follows:

- Vital signs (BP, pulse, temperature)
- Blood sample collection for analysis at central laboratory (eGFR)
- FMV urine sample collection
- Concomitant medication
- AEs
- Confirmation of completed follow-up visit using IRT
- Assessment of vital status will occur at 6 and 12 months post study

### **9.2.5 Unscheduled Visit**

Unscheduled visits may be performed during the course of the study for safety reasons. An unscheduled visit is required 2 weeks after dose reduction at any time during the study. Only the data relevant to the purpose of the visit will be collected in the source documents and eCRF. An unscheduled visit is requested in the following cases:

- QTcF value exceeding 500 msec, or an increase  $>60$  msec from baseline, where the ECG will be repeated (confirmed) at an unscheduled visit
- Systolic BP is  $\geq 165$  mmHg or diastolic BP is  $\geq 105$  mmHg, or confirmed systolic BP  $>130$  mmHg or a diastolic BP  $>80$  mmHg
- Decrease in eGFR  $>30\%$  compared to baseline, or a confirmed decrease in eGFR  $>20-30\%$  compared to baseline (detailed in Section [7.6.1, Deterioration in Renal Function](#))

Additional unscheduled visits may be planned per Investigator's judgment.

## **9.3 Study Specific Assessment Procedures**

### **9.3.1 Health-related Quality of Life Assessments (HRQoL)**

#### **9.3.1.1 Short Form Health Survey (SF-36)**

The SF-36 HRQoL assessment is a 36-question subject HRQoL questionnaire and is presented in [Appendix 8](#).

### **9.3.2 Healthcare Resource Utilization (HRU) Assessment**

The collection of information on HRU will be collected at the time points specified in the [Schedule of Events](#) (Month 12, provided from the results of Week 52/ End of Treatment Visit of the AURORA 1 study, and at Months 15, 18, 21, 24, 27, 30, 33, and 36) and documented in the electronic data capture (EDC) system. This information will be collected via interview of the subject by the study staff and entered into the EDC system. General information collected may include:

- Type of insurance coverage
- Number of visits to ANY health care professionals (HCP), other than study doctor
- Types of HCP visited (specialists versus primary care)
- Time spent on visits
- Diagnostic tests performed
- Time spent by caregivers assisting patient with HCP visits (can ask general question if subject required a family member or other person to assist them to attend the visit)
- Prescriptions issued, filled
- Community services used

## **10. EVALUATION, RECORDING AND REPORTING OF AEs AND SAEs**

### **10.1 Definitions**

#### **10.1.1 Adverse Event**

Any untoward medical occurrence in a subject administered a pharmaceutical product and which does not necessarily have a causal relationship with this treatment is an AE. An AE can therefore be any unfavorable and unintended sign (including an abnormal laboratory finding), symptom, or disease temporally associated with the use of a medicinal (investigational) product, whether or not related to the medicinal (investigational) product.

#### **10.1.2 Adverse Drug Reaction**

In the pre-approval clinical experience with a new medical product or its new usages, particularly as the therapeutic dose(s) may not be established, all unintended responses to a medicinal product related to any dose should be considered adverse drug reactions (ADRs). The phrase “responses to a medicinal product” means that a causal relationship between a medicinal product and an AE is at least a reasonable possibility, i.e., the relationship cannot be ruled out.

#### **10.1.3 Serious Adverse Event**

An SAE (experience) or reaction is an untoward medical occurrence that at any dose meets 1 or more of the following criteria:

- Results in death (Note: death is an outcome, not an event)
- Is life-threatening (Note: the term “life-threatening” refers to an event in which the subject was at immediate risk of death at the time of the event; it does not refer to an event which could hypothetically have caused a death had it been more severe)
- Requires in-patient hospitalization or prolongation of existing hospitalization
- Results in persistent or significant disability/incapacity
- Results in a congenital anomaly/birth defect
- Is a medically important event or reaction

The definitions and reporting requirements of International Council for Harmonisation (ICH) Guidelines for Clinical Safety Data Management, Definitions, and Standards for Expedited Reporting, Topic E2 will be adhered to.

Medical and scientific judgment must be exercised in deciding whether expedited reporting is appropriate in other situations, such as important medical events that may not be immediately life-threatening or result in death or hospitalization but may jeopardize the subject or may require intervention to prevent one of the other outcomes listed in the definition above. These will also usually be considered serious.

Hospitalizations for elective or previously scheduled surgery for pre-existing conditions, which have not worsened after initiation of treatment, will not be classed as SAEs. Previously scheduled hospitalizations must be documented in the subject's source documents before the subject signed the informed consent form (ICF). A kidney biopsy performed as part of the study to verify eligibility will not be considered an SAE. Any complication experienced during a kidney biopsy procedure resulting in hospitalization or a prolongation of the hospitalization requires SAE reporting.

#### **10.1.4 Suspected Unexpected Serious Adverse Reaction**

Any ADR that is both serious and unexpected (per the IB) that, based on the opinion of the Investigator or Aurinia, is felt to have a reasonable suspected causal relationship to a medicinal product is a suspected unexpected serious adverse reaction.

### **10.2 Adverse Event Descriptors**

#### **10.2.1 Intensity/Severity Categorization**

The term "severe" is often used to describe the intensity (severity) of a specific event (as in mild, moderate, or severe myocardial infarction); however, the event itself may be of relatively minor medical significance (such as severe headache). This is not the same as "serious," which is based on subject/event outcome or action criteria usually associated with events that pose a threat to a subject's life or functioning. Seriousness (not severity) serves as a guide for defining regulatory reporting obligations.

In general, the intensity of a particular AE to be recorded is the worst intensity experienced by the subject during the course of the event. The medical assessment of intensity will be determined by using the following definitions:

- Mild: The AE is easily tolerated and does not interfere with usual activity.
- Moderate: The AE interferes with daily activity, but the subject is still able to function.
- Severe: The AE is incapacitating and the subject is unable to work or complete usual activity.

## 10.2.2 Causal Relationship Categorization

An Investigator who is qualified in medicine must make the determination of relationship to the study treatment for each AE and SAE. The Investigator must decide whether, in his or her medical judgment, there is a reasonable possibility that the event may have been caused by the study treatment. If there is no valid reason for suggesting a relationship, then the AE/SAE must be classified as not related. Otherwise, if there is any valid reason, even if undetermined or untested, for suspecting a cause-and-effect relationship between the study treatment and the occurrence of the AE/SAE, then the AE/SAE will be considered related. For SAEs, the Investigator must provide a brief comment explaining the rationale of his/her assessment of causal relationship on the SAE reporting form.

The following additional guidance may be helpful:

Term	Relationship	Definition
Related	Yes	The temporal relationship of the clinical event to study drug administration indicates a causal relationship, and other drugs, therapeutic interventions or underlying conditions do not provide a sufficient explanation for the observed event.
Not related	No	The temporal relationship of the clinical event to study drug administration does not indicate a causal relationship, or other drugs, therapeutic interventions or underlying conditions provide a sufficient explanation for the observed event.

If the causal relationship between an AE/SAE and the study treatment is determined to be “related”, the event will be considered to be related to study treatment for the purposes of expedited regulatory reporting. In circumstances where the Investigator has not yet provided his/her assessment about the relationship, the event will be considered as “related” and qualify for expedited regulatory reporting.

## 10.2.3 Outcome Categorization

Outcome may be classified as recovered without sequelae; recovered with sequelae; improved; worsened; ongoing; ongoing at End of Study; fatal; or unknown. If the outcome is reported as recovered with sequelae for an SAE, the Investigator should specify the kind of sequelae on the SAE reporting form. SAEs that are ongoing at the time of death will have an outcome of “unknown” recorded. SAEs resulting in a fatal outcome will have an outcome of “fatal” recorded.

## 10.2.4 Symptoms of the Disease Under Study

Symptoms and fluctuations in laboratory parameters related to the disease under study will not be classed as AEs as long as they are within the normal day-to-day fluctuation of the disease. An explanation of these circumstances must be written in the source documents.

Worsening of the symptoms or laboratory parameters however, will be recorded as an AE, and clearly marked as worsening or by the subject's worst observed intensity. The Investigator will be required to assess the relationship to disease under study for each AE as related or not related. An AE will not be able to be assessed as related to both disease under study and related to study treatment.

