Any SAE considered to have a causal relationship (i.e., “related”) to the study treatment and discovered by the Investigator at any time after the study will be reported. A rationale for the assessment of a causal relationship must be provided by the Investigator. The Investigator will also be required to assess the relationship to disease under study for each SAE as related or not related. An SAE will not be able to be assessed as related to both disease under study and related to study treatment. Any safety information that is obtained after the Follow-up Visit (Visit 24) will be documented in the safety database only.

A death occurring during the study or which comes to the attention of the Investigator within 30 days after the last study visit (including the Follow-up Visit) or until 30 days after the last study treatment administration, whichever is longer, whether considered treatment-related or not, must be reported to Aurinia-. If the subject died, the SAE report should include the cause of death as the event term and whether or not the death was related to study treatment, as well as the autopsy findings, if available. Preliminary reports will be followed by detailed descriptions which will include copies of hospital case reports, autopsy reports/certificates and other documents when requested and applicable.

Additional follow-up information must be reported in the eCRF within 24 hours of awareness following Investigator (or site) awareness of the information. The Investigator should not delay reporting an SAE in order to obtain additional information. Additional information, when available, should be reported to [REDACTED] by the reporting procedures described above.

The Investigator is encouraged to discuss with the study Medical Monitor when the issue of seriousness is unclear or questionable.

An Investigator who receives an Investigator safety report describing an SAE or other specific safety information (e.g., summary or listing of SAE) from the sponsor will file it along with the IB and will notify the IRB/IEC, if appropriate according to local requirements.

The sponsor or its representative will be responsible for determining and, in turn, reporting SAEs to regulatory authorities according to the applicable regulatory requirements.

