6.2.16 Adverse Events

An AE with missing intensity of AE will be coded “Severe” which is the worst case. An AE with a missing relationship to Study Drug will be coded as “Related”. An AE with missing relationship to disease under Study will be coded as “Related” to the disease unless the AE is recorded as being related to treatment.

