6.11.7 Other Secondary Endpoints

Not applicable.

QMD Ref: [REDACTED]	Effective: 12Aug2019	Governing QMD: [REDACTED]
Confidentiality Statement		
This document is the property of [REDACTED] and may not be duplicated, copied, altered or removed from company without prior approval from [REDACTED] or in compliance with [REDACTED].		
REF: [REDACTED]		Page 27 of 37

		Controlled Quality Management Document	
		Sponsor:	Aurinia Pharmaceuticals
		Protocol Number:	AUR-VCS-2016-02
STATISTICAL ANALYSIS PLAN. PHASE 2-3-4			

A treatment-related TEAE is defined as a TEAE that is assessed by the Investigator or Sponsor as being related to study drug. If a TEAE has a missing relationship to study drug it is assumed to be related to the study drug for analysis purposes.

A disease-related TEAE is defined as a TEAE that is assessed by the Investigator or Sponsor as being related to the disease under study. If a TEAE has a missing relationship to the disease under study it is assumed to be related to the disease under study for analysis purposes.

Missing severity assessments will be summarised as severe.

Adverse event tables will comprise tables summarizing AURORA 2 TEAEs as well as some tables summarizing all TEAEs from month 0 to month 36.

The following tables will be presented for AURORA 2 TEAEs:

- Summary table of overall incidence, the number of events, relative risk and 95% CI (voclosporin:placebo) including the following top line summaries:
 - Any AE
 - Any TEAE
 - Any Treatment-Related TEAE
 - Any Serious TEAE
 - Any Treatment-Related Serious TEAE
 - Any TEAE Leading to Voclosporin/Placebo Modification
 - Any TEAE Leading to Voclosporin/Placebo Discontinuation
 - Any TEAE Resulting to Death
 - Disease-Related TEAE
 - Disease-Related Serious TEAE
- TEAEs by System Organ Class and Preferred term
- TEAEs by System Organ Class, Preferred term and severity
- Treatment-Related TEAE by System Organ Class and Preferred Term
- Treatment-Related TEAE by System Organ Class, Preferred Term and Severity
- TEAE by System Organ Class and Preferred Term Leading to Dose Modification
- TEAE by System Organ Class and Preferred Term Leading to Voclosporin/Placebo Discontinuation
- TEAE by System Organ Class and Preferred Term Resulting in Death
- Disease-Related TEAE by System Organ Class and Preferred Term
- Serious TEAE by System Organ Class and Preferred Term

QMD Ref: [REDACTED]	Effective: 12Aug2019	Governing QMD: [REDACTED]
Confidentiality Statement		

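### Protocol 10.2.4 and 10.3.2 bar rating an event as related to both disease and study drug, in conflict with the causality standard of 10.2.2 and with no rule for which attribution prevails

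*Protocol*

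**What the plan says.** **The exclusivity rule.** Protocol 10.2.4 asks the investigator to judge each AE as related or not related to the disease under study, and adds: "An AE will not be able to be assessed as related to both disease under study and related to study treatment". Protocol 10.3.2 says the same for serious events: "An SAE will not be able to be assessed as related to both disease under study and related to study treatment".

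**The causality standard.** The governing sentence of Protocol 10.2.2 makes an event related to study treatment "if there is any valid reason, even if undetermined or untested, for suspecting a cause-and-effect relationship between the study treatment and the occurrence" of the event. The definition of an adverse drug reaction in 10.1.2 is similarly broad: a causal link "is at least a reasonable possibility, i.e., the relationship cannot be ruled out". A guidance table in 10.2.2 adds that an event may be rated not related where "other drugs, therapeutic interventions or underlying conditions provide a sufficient explanation for the observed event".

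**Imputation in the SAP.** Both SAP passages code a missing drug relationship as related. They differ on a missing disease relationship. Section 6.2.16 codes it as related "unless the AE is recorded as being related to treatment". The adverse event text of section 6.12.1 gives no such exception: "If a TEAE has a missing relationship to the disease under study it is assumed to be related to the disease under study".

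**The concern.** The protocol treats the two possible causes as overlapping in the area that matters most for this drug. Section 2.1 calls the blood pressure and renal function risks dose-related. Section 7.6.1.1 lists lupus renal flare among the factors that may contribute to a fall in eGFR. For such an event an investigator may reasonably suspect both drug and disease. Under 10.2.2 the drug suspicion alone makes the event related to treatment. Under 10.2.4 and 10.3.2 one of the two attributions must then be denied, and no section says which.

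At stake is the accuracy of the drug-causality field. It defines the treatment-related TEAEs in the SAP, and under 10.2.2 a rating of related qualifies the event for expedited regulatory reporting. In a long-term study whose primary objective is safety, readers will look at the treatment-related displays. A field that cannot record a dual cause makes those displays hard to interpret.

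**Working it through.** The plan gives no figure to reproduce, so the check is mainly a reading of the texts against each other.

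**1. Can both rules be met when drug and disease are both suspected?**

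| Investigator's entry | Protocol 10.2.2, governing sentence | Protocol 10.2.4 / 10.3.2 |
|---|---|---|
| Drug yes, disease yes | Met | Barred |
| Drug no, disease yes | Not met: a valid suspicion of the drug is denied | Met |
| Drug yes, disease no | Met | Formally met, but the disease assessment is recorded wrongly |

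No entry records both judgements correctly. The third row satisfies the letter of both rules, but nothing directs the investigator to it.

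**2. Does the 10.2.2 guidance table settle it?** Only in part. It supports a rating of not related when an underlying condition is a sufficient explanation. It does not reach the case where disease contributes without fully explaining the event. The exclusivity sentences apply there too.

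**3. Where is the drug field used?** In the SAP adverse event text (6.12.1) it feeds two top-line rows (treatment-related TEAEs and treatment-related serious TEAEs), four AURORA 2 tables (each of these by system organ class and preferred term, with and without severity) and two displays by year of onset. It also feeds expedited reporting through Protocol 10.2.2.

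**4. What does SAP imputation do?**

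| Recorded | SAP 6.2.16 | SAP 6.12.1 text |
|---|---|---|
| Disease yes, drug missing | Both related | Both related |
| Disease missing, drug yes | Exception applies: disease not imputed as related | Both related |
| Both missing | Both related, if an imputed drug rating does not count as recorded | Both related |

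So the SAP can create the pair that the protocol forbids, and its two passages disagree in the second row. None of these cases removes an event from a treatment-related table.

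**5. Illustration of size.** Protocol 1.2.5 reports Phase 2 discontinuations for decreased GFR: 7 (7.9%) on low dose and 1 (1.1%) on placebo. The 7.9% implies n = 89. Placebo n = 88 is an assumption (87 to 95 all give 1.1%). These are discontinuations, not treatment-related rates, and serve only as a scale. Let f be the share of such events rated as disease only; the documents do not give f.

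- Equal share in both arms: active rate = (7/89)(1 − f), placebo rate = (1/88)(1 − f). The factor cancels in the ratio.
- Active arm only: the placebo rate stays at 1/88.

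| f | Equal share: rates | Difference (points) | Ratio | Active only: difference (points) | Ratio |
|---|---|---|---|---|---|
| 0% | 7.9% v 1.1% | 6.7 | 6.92 | 6.7 | 6.92 |
| 10% | 7.1% v 1.0% | 6.1 | 6.92 | 5.9 | 6.23 |
| 25% | 5.9% v 0.9% | 5.0 | 6.92 | 4.8 | 5.19 |
| 50% | 3.9% v 0.6% | 3.4 | 6.92 | 2.8 | 3.46 |
| 75% | 2.0% v 0.3% | 1.7 | 6.92 | 0.8 | 1.73 |

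The SAP's top-line AE summary reports a relative risk, which would not move under an equal share. In a blinded study, reassignment confined to the active arm is an extreme case.

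**The case against.** The best defence has four parts.

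- **The rule is symmetric.** It does not say that disease wins. An investigator who applies 10.2.2 first records drug as related and disease as not related, and breaks no rule. The imputation in SAP 6.2.16 also leans towards the drug. This stands: a bias away from the drug is not shown, only a forced choice without a tie-break.
- **The guidance table supports exclusivity.** It does so where disease is a sufficient explanation, but not where disease is only contributory. Also, the cannot-be-ruled-out wording of 10.1.2 defines an adverse drug reaction. The investigator's own test is in 10.2.2, and the conflict rests on that section.
- **Expedited reporting has backstops.** All SAEs go to the safety desk within 24 hours whatever the attribution (10.3.2). Unassessed events count as related (10.2.2). The opinion of the investigator or the sponsor is enough for a suspected unexpected serious reaction (10.1.4), which must also be unexpected per the Investigator's Brochure. A reader might infer that a serious unexpected event rated as disease-related would escape expedited reporting. The documents do not support that; only the trigger based on the investigator's rating is lost.
- **Most safety output is untouched.** The primary AE estimand (SAP 3.1) is the proportion of subjects reporting AEs. The all-TEAE, serious, discontinuation and death tables, the exposure-adjusted rates and the eGFR analyses do not use the drug field. An event rated as disease still appears in the disease-related tables. The SAP also lets the sponsor's rating make a TEAE treatment-related. Renal response (SAP 6.11.1) treats disease-related and treatment-related eGFR events alike, so the choice does not alter it.

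These points limit the harm. They do not repair the investigator's field.

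**Conclusion.** The conflict holds as a defect in the recording rule. Two protocol sentences prohibit an answer that the governing sentence of 10.2.2 may require, and no precedence is stated. The consequence is a possible loss of events from the treatment-related TEAE displays and from the investigator-based reporting trigger, most plausibly for falls in eGFR. The SAP inconsistency on a missing disease relationship is separate and needs correcting in any case. It rests on partial text, because the opening of section 6.12.1 is not in the text available for review.

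Neither the size nor the direction of miscoding can be derived from the documents. The table of shares shows only how absolute rates and the risk difference would respond to an assumed f.

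Two stronger readings should be resisted. A reader might infer that the rule systematically hides drug toxicity, but it is symmetric and nothing shows how investigators choose. A reader might also point to the Phase 2 deaths (10 low dose, 2 high dose, 1 placebo), all judged unrelated to treatment. Those come from another study, nothing says this rule applied there, and Protocol 1.2.5 says its data and safety monitoring board also judged them unrelated.

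The change should be made, but the primary safety comparison does not depend on it.

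**What to change.** **Protocol.** Delete the exclusivity sentences in 10.2.4 and 10.3.2. State that relationship to study treatment and relationship to disease are two independent yes/no questions, and that the drug question follows the governing sentence of 10.2.2 whatever the disease answer. Reword the 10.2.2 guidance table to match. If the sponsor prefers to keep exclusivity, the minimum is a sentence saying that a valid suspicion of the drug prevails.

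**Data capture.** Remove any data-entry check that enforces exclusivity. The wording hints at one, but the documents describe none.

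**SAP.** Let an event appear in both the treatment-related and the disease-related tables. Use one rule for a missing disease relationship in 6.2.16 and 6.12.1. With independent questions, the natural choice is to drop the exception in 6.2.16.

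**Cost.** A few sentences in each document and possibly a database change, with no added visits, subjects or procedures. Treatment-related counts would rise slightly and somewhat more events would qualify for expedited reporting.
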